Hypothesis: We hypothesize that children with CF and fungal infections without ABPA will have elevated allergic inflammatory profiles and increased sensitization to fungal elements compared to those without fungal infection.

Specific Aims:

- **Specific Aim 1:** Compare Th2 inflammation in patients with and without fungal infections in patients with CF and to those with ABPA.
 - Approach: We will obtain serum and sputum samples from 25 patients with either (1) fungal infection without ABPA, n=10 (defined as \geq two positive fungal cultures in prior 18 months), (2) no fungal infection, n=10, and (3) ABPA, n=5, and measure specific sputum and serum cytokine measurements to evaluate Th2 and Th1 inflammatory pathways.
 - Biomarkers measured: Eosinophilic cationic protein (ECP), Interleukin-4 (IL4), Interleukin-5 (IL5), Interleukin-10 (IL10), Interleukin-13 (IL13), and eosinophil count in both serum and sputum.
 - Expected outcome: Individuals with fungal infection without APBA will have elevated Th2 markers of inflammation compared to those with no fungal infection. We will also compare to those with ABPA as a separate control group. We will also measure Th1 markers to be used as a reference to previously established inflammatory profiles seen in CF, seeing if those with fungal disease deviate towards a more Th2 driven process.
- **Specific Aim 2:** Investigate allergic sensitization to fungal elements in patients with CF fungal infection without ABPA compared to those without fungal infection and to those with ABPA.

- Approach: We will measure total IgE and serum ImmunoCAP testing of specific IgE levels to fungal proteins of various species (*Aspergillus*, *Candida*, etc). to determine fungal sensitization. We will also survey patients regarding environmental exposures to explore relationships with allergic sensitization.
- Expected outcome: Individuals with fungal infection without ABPA will be more likely to show allergic sensitization to fungal elements when compared to those with no fungal infection.

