Sample Size Estimates: Power and sample size for the study proposal is fixed due to the expected number of eligible patients to be recruited into this pilot study during the study window. Based on preliminary data and the described definitions of types of infection, investigators anticipate that over a 1-year recruitment window they will be able to enroll approximately 10 individuals with no fungal infection, 10 patients with a fungal infection but not ABPA and 5 with ABPA. The primary analysis plan focuses on the description and comparison of key plasma and sputum measures described in Table 3. Power analysis provides the detectable effect sizes when comparing the control arm (no fungal infection) to either the non-ABPA group or the ABPA group. Calculations are based on a power of 80% and Type I error rate of 0.05 for two-sided two-sample equal-variance t-test conducted in PASS version 15 statistical software (2). Group sample sizes of 10 and 5 in the fungal infection groups achieve 80% power to reject the null hypothesis of zero effect size when the population effect size is 1.36 and 1.66 respectively. Thus, the study is powered at 80% to detect a difference in the mean markers to be measured greater than 1.66 and 1.32 standard deviations. Given limited data in the literature regarding Th2 markers in CF, we are basing these calculations off of deviations from a mean for the multiple Th2 markers we are testing.

Study Visit: We plan to prospectively recruit 25 subjects with CF during a period of clinical stability. Subjects will have one research clinic visit that will coincide with their clinic visit at CHCO Pulmonary Clinic facilities. The following diagnostic information will be entered onto Case Report Forms: demographic information, diagnostic history and mutations, CF-related co-morbidities, historic microbiology results including fungal culture results, medications including modulator therapy and long-term antibiotic regimens, previous allergy testing, diagnostic criteria for ABPA (if applicable). We will also utilize historical clinical data from the medical record to establish other co-morbidities, lung function trends and baseline, history of other bacterial infections, history of allergy diagnoses, and other pertinent medical history and diagnostic testing (ie previous CT scan results, previous blood work, etc.). The following evaluations will be performed (Table 2, Figure 2):

- Historical data in the medical record

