 - Examples include Co-morbid diagnoses related to CF (such as but not limited to CF related diabetes, CF liver disease, asthma, etc), previous blood work (such as but not limited to serum IgE levels, previous allergy testing, bronchoscopy data and lavage studies, routine and urgent/admission CF labs, etc), previous spirometry and lung function data, previous nutritional and growth data (BMI, vitamin levels, etc), previous microbiology and culture data, etc.
- BMI measurements obtained from regular CF clinic visit

Table 2. Study Activities During Visit

Study Activities	Perform at Visit
Informed consent	x
History and physical	x
BMI Measurement	x
Environmental Questionnaire	x
Spirometry	x
Induced Sputum Collection	x
Blood Draw	x

Table 3. Biomarkers to be studied. IL4, IL5, and ECP measurements are priority for Th2 assessment. NE, IL8, IL-1B are priority for Th1 assessment.

Sputum	Serum

 • Culture for CF pathogens • Culture for fungi • Cell count with differential 	
 Th1 pathway 
 • IL8, IFNY • NE-APC Th2 pathway 
 • IL4, IL5, IL10, IL13 • ECP • Total IgE • Fungal panel (Table 4) Other 
 • CBC with diff • Vitamin D • Calprotectin • High-sens CRP

 Th1 pathway 
 • IL8, IFNY, IL-1B • NE Th2 pathway 
 • IL4, IL5, IL10, IL13 • ECP 	Aliquot frozen and banked
Aliquot frozen and banked	

- Height and weight to be obtained and subsequently calculated.
 - Pulmonary function testing obtained from regular CF clinic visit
 - Spirometry will be performed according to American Thoracic Society criteria, while absolute values will be converted to percent predicted using the Global Lung Function initiative reference equations¹⁷.
 - Sputum collection
 - Spontaneously expectorated sputum will be used as possible
 - This will be collected at home by the patient following a routine respiratory airway clearance regimen within 12 hours of clinic visit. The sample will be placed in a mailed specimen cup and placed on ice and brought to the clinic visit
 - If sputum is not able to be expectorated prior to visit, we will attempt to utilize remaining sputum expectorated that is not used for clinical needs for further analysis and storage

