Rationale: Studies have shown increased rates of atopy, asthma, and fungal allergen sensitization in adults with CF, yet the impact of this is not clearly understood^{14, 15}. There have been few studies in pediatrics with little understanding of when this sensitization develops and the changes in outcome measures that may be the result of a more allergic airway in the setting of CF. Furthermore, ABPA is a known severe condition that individuals with CF can develop, yet the timeline and predisposition that patients face is unclear. Given this, allergic sensitization to fungal elements in the environment may be playing a reactive role in the CF airway and provide clues to the development of ABPA, asthma, and other pulmonary sequelae.

Study Design and Visit: Described fully under specific aim 1, discussing patient criteria, inclusion, and study operations. Serum ImmunoCAP samples will be collected under the same blood draw as described in the study design. Specific panel to be collected described in Table 4.

Statistical Analysis: Will utilize descriptive statistics and associations of each group as well as differences between groups. Will utilize a biostatistician to help with data analysis, organization, and reporting.

Specific Aim 1: Compare Th2 inflammation in patients with and without fungal infections in patients with CF.

- Individual markers: We will use descriptive statistics to measure the differences between each individual marker in both the sputum and serum between groups. We will further look at associations with serum and sputum measurements in each group.
- Clinical and Environmental characteristics: We will use descriptive statistics to account for differences and associations in lung function and BMI between groups. We will also account for differences in individuals by other co-infections (*Pseudomonas*, MRSA, etc.) in our analysis and study these associations as well. Given that ABPA individuals will be harder to recruit, we will do our best to control based upon individuals recruited into this group.

This is a pilot and discovery study searching for possible Th2 markers to further study and use clinically. Given this, our goal is to detect as many possible markers as we can feasibly study and thus why we will not initially be correcting for multiple comparisons.

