Storage of Data: Data will be entered from the CRF's and stored in electronic format using REDCap (Research Electronic Data Capture). Hard copies of the CRF will be kept in a secure location at the site of collection for data entry verification. REDCap is a secure, web-based application designed exclusively to support data capture for research studies. REDCap provides: 1) an intuitive interface for data entry with data validation, 2) audit trails for tracking data manipulation and export procedures, 3) automated export procedures for seamless data downloads to common statistical programs (SPSS, SAS, Stata, R), 4) procedures for importing data from external sources, and 5) advanced features such as branching logic and calculated fields.

Potential Scientific Problems.

Limitations: This is a single center cross sectional pilot study, thus our findings will be preliminary but may inform future larger studies. All patients will likely continue to follow clinically at the CHCO CF center, however this is a one-time study visit with one time point of data collection. We will do our best to control for age, disease severity (BMI, lung function), sex, and other demographic factors between groups, however it has been shown that individuals with ABPA and fungal infection CF are often older than those without fungal infection. This study is being performed in patients with clinical stability. Inflammatory changes may be more dynamic and evident during acute illness and undetectable during baseline status. We will attempt to account and analyze the effects of other bacteria or infectious organisms to the best of our ability. This study will mainly involve pediatric patients of various age groups, which may be difficult to translate to adult outcomes and disease. We may find that fungal infection without ABPA induces a Th1 response rather than Th2 contrary to our hypothesis; however this will still provide important information regarding the role of fungi in CF lung disease.

Data Analysis Plan.

Analysis of Study Results: Will utilize descriptive statistics and associations of each group as well as differences between groups. Will utilize a biostatistician to help with further analysis and data analysis, organization, and reporting.

- Individual markers: We will use descriptive statistics measure the differences and associations between each individual marker between groups.

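### Aim 1's secondary question, whether fungal disease shifts inflammation towards Th2 relative to Th1, has no analysis that compares the two pathways directly

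*Combined protocol and SAP*

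**What the plan says.** - **The question.** Specific Aims, Aim 1, Expected outcome: the main expectation is higher Th2 markers in fungal infection without ABPA than in patients without fungal infection. Th1 markers are added as a reference, "seeing if those with fungal disease deviate towards a more Th2 driven process". Limitations allows for the opposite result: "We may find that fungal infection without ABPA induces a Th1 response rather than Th2 contrary to our hypothesis".
- **The markers.** Table 3 gives priority to IL4, IL5 and ECP for Th2, and says "NE, IL8, IL-1B are priority for Th1 assessment". The sputum Inflammatory Indices paragraph names the same six.
- **The analysis.** Statistical Analysis, Aim 1: "We will use descriptive statistics to measure the differences between each individual marker in both the sputum and serum between groups". The general paragraph specifies ANOVA with pairwise differences, or Welch, Wilcoxon or Fisher tests, each at 0.05. No ratio, difference score or group-by-pathway term is defined.
- **Where the pathways meet.** The Immune Profile, a secondary outcome, classes each marker category as elevated or depressed once the single-marker results are in. It has no threshold and no test of a relative shift.
- **Outcome list.** The primary outcome holds sputum Th2 markers only. Th1 markers have their own outcome line only for serum, although Table 3 also measures them in sputum.

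**The concern.** A statement that one pathway moved more than another needs a comparison of the two movements. Separate tests give two verdicts against zero, and a difference between those verdicts is not a test of the difference. With 10 patients per group, single-marker tests often disagree by chance even when the true rises are equal. A general rise in airway inflammation could then be reported as a Th2 shift, or as a Th1 shift in the mirror-image case. The protocol's rationale links an allergic mechanism to readier use of steroids and antifungals, so the wording of this finding may carry weight beyond a pilot.

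**Working it through.** **Inputs from the documents.** Group sizes: "approximately 10 individuals with no fungal infection, 10 patients with a fungal infection but not ABPA and 5 with ABPA". Test: "Calculations are based on a power of 80% and Type I error rate of 0.05 for two-sided two-sample equal-variance t-test". **Assumed, because the documents give neither:** size of rise, and correlations between markers.

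**1. The plan's own figure.** Noncentral t, noncentrality d·√(n₁n₂/(n₁+n₂)).
- 10 v 10: 18 df, d × 2.236; 80% power at d = 1.325.
- 10 v 5: 13 df, d × 1.826; 80% power at d = 1.660.

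These match "greater than 1.66 and 1.32 standard deviations". The preceding sentence has "when the population effect size is 1.36 and 1.66 respectively"; at 1.36, 10 v 10 has 82.0% power. The 1.36 and 1.32 should be reconciled, but nothing below depends on it.

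**2. One Th2 and one Th1 marker, equal true rise.** Single-marker power p is 18.5%, 56.2% and 79.7% at 0.5, 1.0 and 1.32 SD. If the markers are independent, Th2 is significant and Th1 is not with probability p(1−p):
- 0.185 × 0.815 = 15%
- 0.562 × 0.438 = 25%
- 0.797 × 0.203 = 16%

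At correlation 0.7, simulation gives 9%, 13% and 9%.

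**3. Three and three priority markers, equal true rise, 10 v 10** (simulation, 40,000 runs). Share of studies with more Th2 than Th1 markers significantly raised:

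| Rise (SD) | 0.5 | 0.8 | 1.0 | 1.3 |
|---|---|---|---|---|
| all correlations 0.3 | 23% | 31% | 31% | 25% |
| all correlations 0.7 | 15% | 22% | 22% | 17% |

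A clear pattern, at least two Th2 markers and no Th1 marker, occurs in about 1–5% under equal correlations. It occurs in roughly 8–14% (rises of 0.5 to 1.0 SD) if the pathways correlate less with each other than within themselves.

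**4. A direct contrast.** C = mean of three Th2 markers minus mean of three Th1 markers, in SD units. With correlation w within a pathway and c across pathways, Var(C) = 2[(1+2w)/3 − c]. With known SDs and an equal rise in all markers, C is falsely positive in about 5% of studies two-sided, or 2.5% in the Th2 direction, which is the like-for-like comparison with step 3. For a Th2-only rise of 1.0 SD the standardised effect is 1/SD(C); the shift detectable at 80% power is 1.325 × SD(C).

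| w, c | SD(C) | Standardised effect | Detectable shift (SD) |
|---|---|---|---|
| 0.3, 0.3 | 0.683 | 1.46 | 0.91 |
| 0.5, 0.5 | 0.577 | 1.73 | 0.76 |
| 0.7, 0.7 | 0.447 | 2.24 | 0.59 |
| 0.5, 0.2 | 0.966 | 1.04 | 1.28 |
| 0.7, 0.3 | 1.000 | 1.00 | 1.32 |
| 0.5, 0 | 1.155 | 0.87 | 1.53 |
| 0.7, 0 | 1.265 | 0.79 | 1.68 |

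With SDs estimated from the 20 patients across both groups, power is 82–99% in the first three rows. In the last four it is about 33–59%, allowing for the choice of scaling, against 56% for a single marker.

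**5. Which SD to divide by.** Under an equal rise, the contrast is falsely positive in 1–4% of studies with the SD across all patients in the comparison, but in 6–16% with within-group or control-group SDs.

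**6. Dilution.** A twofold dilution moves every log marker by ln 2 = 0.693. Unstandardised, the contrast moves by 0.693 − 0.693 = 0. Standardised, with assumed log SDs of 0.5 (Th2) and 1.0 (Th1), it moves by 0.693/0.5 − 0.693/1.0 = 0.69. If one group is diluted, the simulated false-positive rate is then 48% at correlation 0.5; log SDs of 0.7 and 1.0 give about 12%.

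**The case against.** The strongest reply is that balance is not what this study is built to test. The hypothesis, the title of Aim 1 and the primary outcome all ask whether Th2 markers are higher than in controls, and between-group tests answer that. The balance clause ends the last sentence of an expected-outcome paragraph, and the Th1-rather-than-Th2 remark is a limitation. The Immune Profile would show a general rise as both pathways raised. The study calls itself a hypothesis-generating pilot, and nowhere says that it will infer a shift by counting significant markers.

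Most of this stands. A reader might infer that the planned analysis cannot answer the study's main question; the documents do not support that. A reader might also take 15–31% as the plan's error rate; it is not, since it belongs to a counting rule that the plan does not contain, and the clearer pattern is much rarer.

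The reply does not remove the gap. The profile is built from single-marker results and has no rule to separate a general rise from a relative one. Pilot status explains the absence of multiplicity correction, but does not license a relative conclusion without a relative comparison. Nor is the choice of markers arbitrary: the plan names the priority set itself.

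**Conclusion.** The point holds as a limited one. The secondary question about Th2 relative to Th1 has no analysis that can answer it; the main hypothesis is unaffected. Under equal true rises, reading significance labels side by side would favour Th2 in about 15–31% of studies by simple count, and in about 1–5% by a clear two-or-more against none pattern (equal correlations). Rises and correlations are assumptions throughout.

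Two stronger readings of the remedy should be avoided. One is that a standardised contrast removes sample dilution: it does so only if the log SDs match, and the documents give no SDs. The other is that the contrast is reliably powerful: power near 90% or above needs the two pathways to correlate with each other about as strongly as markers within a pathway do, and the documents give no correlations. The fair range for a 1.0 SD rise in Th2 alone is roughly 33–99%.

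**What to change.** Add one exploratory sputum analysis to the Statistical Analysis section and list it under Outcome Measures.

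- For each patient, take the mean of log IL4, IL5 and ECP minus the mean of log IL8, IL-1B and NE. Standardise each log marker by its SD across all patients in the comparison.
- Compare fungal infection without ABPA with controls, and report the difference with a 95% confidence interval.
- As a sensitivity analysis, report the same contrast of unstandardised logs, the only version that cancels sample dilution.
- Tie any wording about a relative Th2 or Th1 shift to this contrast, read alongside the single-marker results. Those are still needed, because a net contrast cannot tell raised Th2 from lowered Th1.

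**Cost:** one derived variable, one comparison and one sensitivity analysis; no new assays, patients or visits, and no change to the fixed sample size. **Downsides:** the three markers in each pathway are weighted equally, and a wide interval is likely if the pathways correlate weakly. An inconclusive contrast should then be reported as such, not as evidence of no shift.

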Fungal Infection group: Have had a fungal species isolated from sputum and/or BAL culture on ≥ 2 separate occasions in the 18 months preceding study visit and do not have a diagnosis of ABPA (N=10).

Control group: Have never previously isolated fungus from sputum, BAL, or OP swab (N=10).

ABPA group: Previous diagnosis of ABPA as defined by CFF guidelines, regardless of the amount of fungal infection or history thereof.

- ABPA Minimum diagnostic criteria per CFF: Acute or subacute deterioration, total serum IgE > 500 IU per mL, immediate cutaneous reactivity to *Aspergillus* or in vitro IgE antibody to *A. fumigatus*, and either a new or recent chest imaging change that has not responded to antibiotics and standard physiotherapy OR precipitin to *A. fumigatus* or IgG antibody to *A. fumigatus*¹ (N=5). Culture positive sputum is not required for ABPA diagnosis and is not taken into account for the diagnosis per CFF guidelines.

Recruitment: We propose to recruit 25 patients with CF aged between 8 and 25 years who agree to participate in this cross-sectional study looking at the immune system characteristics of fungal infection and ABPA. We plan to screen individuals coming to their routine CF clinic and approach them regarding their interest in participating in this study. From this, we will explain the concept, hypothesis, and procedures involved with intent to schedule them for a research visit.

Patient Selection: Patients will be recruited from the CF Center at CHCO by study investigators or qualified research coordinators at the time of a routine clinic visit.

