Pulmonary Function Testing: Spirometry will be performed according to American Thoracic Society Guidelines¹⁹. The indices measured during the testing include forced expiratory volume in 1 second (FEV1), forced vital capacity (FVC), FEV1/FVC ratio and mid-volume forced expiratory flow (FEF25-75). Our pulmonary function laboratory has been used in a number of studies of CF^{12, 20, 21}. The anticipated risks involved with this procedure are a temporary increase in cough and shortness of breath. To minimize this risk, we will encourage the subject to take big breaths and take breaks between coughing to reduce the tendency to develop gagging or violent coughing. Pulmonary function testing is a part of the standard clinical care for patients with cystic fibrosis.

Blood draw: This will be performed per standard operating procedure of the CHCO clinical and research laboratory sites utilizing patient samples and body fluids. Sterile technique with fresh needles and devices will be used in to minimize infection risk. Trained nursing staff and/or phlebotomists will be the ones performing the blood draw in a CHCO approved environment for proper drawing and handling of specimens. Using these individuals will also minimize the risk for local trauma, bruising, and/or injury that is possible with routine blood draws.

The following testing will be performed on all serum samples:

- **Inflammatory Indices:** Serum samples will be sent to the Core and Clinical Laboratory to measure various systemic markers of inflammation (Table 3) which are thought to reflect clinical parameters in CF. The main markers of Th2 inflammation to investigate are: IL4, IL5, and ECP. The main markers of Th1 inflammation to investigate are: IL8, IFNY, NE-APC.
- **Mold Panel:** A panel of allergic sensitization (IgE levels) to various environmental fungi and molds will be sent on serum samples, along with a total IgE sample (Table 4).
- **Banking of samples to be used for molecular identification of bacteria/fungus and Molecular identification of transcription factors/gene signaling:** All remaining serum and sputum samples will be stored in the appropriate storage device and temperature in the CF research teams designated sample storage area for later analysis utilizing transcriptomics, proteomics, and/or microbiome analysis.

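### The fungal infection without ABPA group is kept free of ABPA only by the absence of a diagnosis, and no step checks that label against the IgE and record data the study collects

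*Combined protocol and SAP*

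**What the plan says.** The Hypothesis section predicts that "children with CF and fungal infections without ABPA will have elevated allergic inflammatory profiles" compared with patients without fungal infection. The group definitions under Specific Aim 1 set the groups as follows.

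- **Fungal infection:** a fungal species cultured from sputum or BAL at least twice in the "18 months preceding study visit and do not have a diagnosis of ABPA (N=10".
- **Control:** no fungus ever isolated from sputum, BAL or oropharyngeal swab. ABPA is not mentioned.
- **ABPA:** "Previous diagnosis of ABPA as defined by CFF guidelines, regardless of the amount of fungal infection or history thereof".

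The inclusion rule that a patient may fit only one fungal group uses these same definitions.

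The minimum criteria listed under the ABPA group have several parts. The first parts are "Acute or subacute deterioration, total serum IgE > 500 IU per mL, immediate cutaneous reactivity to *Aspergillus* or in vitro IgE antibody to *A. fumigatus". One more part is needed as well: "either a new or recent chest imaging change that has not responded to antibiotics and standard physiotherapy OR precipitin to *A. fumigatus". A positive IgG result for that species can stand in for the precipitin. The same paragraph says that a positive culture is not needed for the diagnosis.

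Under Study Visit, the case report form records "previous allergy testing, diagnostic criteria for ABPA (if applicable"). Past CT results and blood work are also taken from the record. Under Blood draw, the Mold Panel entry reads "A panel of allergic sensitization (IgE levels) to various environmental fungi and molds will be sent on serum samples, along with a total IgE sample", and Table 4 lists *A. fumigatus* as m13. These tests appear only as outcomes. Neither Statistical Analysis nor Limitations mentions unrecognised ABPA.

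**The concern.** The words *without ABPA* carry the inference. The plan already expects raised sputum Th2 markers in ABPA (Outcome Measures), so finding them there would be no surprise. What would be new is finding them in fungal infection without ABPA.

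A patient with repeated positive cultures who meets the full minimum criteria, but whom no one has diagnosed, is enrolled as non-ABPA. Nothing requires the criteria to be completed for that patient. Such patients pull the fungal group's Th2 markers up, which is the direction predicted. Aim 2 is exposed too, because total IgE and *Aspergillus* IgE are both ABPA criteria and sensitization measures.

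The background section says that a Th2 finding may lead to readier use of steroids and antifungals. The pilot will also choose which markers to pursue. Both uses suffer if the signal comes from a few unrecognised ABPA cases.

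**Working it through.** **1. The plan's own figures.** Sample Size Estimates uses a two-sided, equal-variance t-test with alpha 0.05 and 80% power. Power is the probability that |T| exceeds t(0.975, df), where T is noncentral t with noncentrality d × √(n1·n2/(n1+n2)).

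- 10 v 10: df 18, √(100/20) = 2.236; 80% power at d = 1.325. The plan's 1.32 reproduces (power 79.7%).
- 10 v 5: df 13, √(50/15) = 1.826; 80% power at d = 1.660. The plan's 1.66 reproduces.
- The same paragraph also gives 1.36 for the 10 v 10 comparison, at which power is 82.0%. The 1.36 and 1.32 should be reconciled, but nothing here depends on it.

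**2. Assumptions.** The documents give neither a rate of unrecognised ABPA nor the size of its Th2 shift. Suppose that k of the 10 fungal-group patients have unrecognised ABPA and are shifted up by D SD, that the rest do not differ from controls, and that no control has unrecognised ABPA. D runs from 1.66 to 3. The lower end borrows the plan's *detectable* difference for ABPA, which is not an expected effect.

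**3. Bias and false positives per marker.** The group mean rises by k × D / 10. The chance of a significant upward result comes from 200,000 simulated 10 v 10 t-tests per setting.

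| k of 10 | Mean shift (SD) | D = 1.66 | D = 2.5 | D = 3 |
|---|---|---|---|---|
| 0 | 0 | 2.5% | 2.5% | 2.5% |
| 1 | 0.17-0.30 | 4.2% | 4.5% | 4.5% |
| 2 | 0.33-0.60 | 7.0% | 8.7% | 9.1% |
| 3 | 0.50-0.90 | 11.9% | 16.6% | 18.8% |

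The Wilcoxon test, which the plan allows, gives slightly lower values: about 4%, 6-7% and 10-13% for k = 1, 2 and 3.

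**4. Averaging over the unknown count.** If each fungal-group patient has probability q of unrecognised ABPA, k is binomial(10, q).

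- q = 5%: the probabilities of k = 0, 1, 2, 3 are 0.599, 0.315, 0.075 and 0.011. At D = 1.66, 0.599 × 2.5 + 0.315 × 4.2 + 0.075 × 7.0 + 0.011 × 11.9 = 3.5%. At D = 3 the result is just under 4%.
- q = 10%: about 5% at D = 1.66 and about 6% at D = 3.
- The chance of two or more such patients among ten is 9% at q = 5% and 26% at q = 10%.

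**5. Equal rates in both groups.** When controls carry unrecognised ABPA at the same rate (2-20%, same shifts), the upward rate stays at 2.3-2.6%. The bias comes from a *difference* in rates.

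**6. Cost of leaving patients out.** Removing 1, 2 or 3 fungal-group patients moves the detectable effect from 1.325 to 1.37, 1.42 or 1.48 SD.

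**The case against.** The strongest reply is that these are clinically stable patients followed at a CF center, so two or three undiagnosed cases in ten may be unlikely. That stands as a limit on size: at 5-10% unrecognised, the per-marker rate moves only from 2.5% to about 3.5-6%, in a study that calls itself hypothesis-generating. It does not show that the label is right, and the plan does not document a check.

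Four stronger readings are tempting, and the documents do not support them.

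- *The error necessarily favours the hypothesis.* ABPA does not require a positive culture and the control definition is silent on it. The one-group rule would stop a diagnosed case from entering as a control, but not an unrecognised one. Equal rates cancel the bias. A higher rate in the fungal group is plausible but assumed.
- *A patient with two cultures, IgE above 500, positive m13 and a recorded deterioration is a mislabelled ABPA case.* Under the protocol's own criteria that is incomplete without the imaging change or precipitin/IgG, and neither is a visit test.
- *The chance of at least one false elevation across the six primary markers reaches 36-72%.* That takes 1-(1-p)^6 with 2 or 3 of 10 mislabelled and independent markers. With an assumed correlation of 0.5-0.7 it is about 20-51%, against 8-11% with no mislabelling. Part of it is multiplicity that the plan openly accepts.
- *A Th2 conclusion should stand only if it survives dropping patients with high IgE and positive m13.* Table 3 lists total IgE as a Th2 marker and fungal IgE is the Aim 2 outcome, so this selects on outcomes. With a true effect of 1.325 SD and an assumed IgE-marker correlation of 0.5-0.7, dropping the top 2-4 of 10 fungal-group patients cuts the estimate to about 0.91-1.16 SD and power from 80% to 41-65%. A real non-ABPA Th2 phenotype could fail such a test.

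**Conclusion.** The gap is real. Group membership rests on whether a diagnosis has been made, and no step compares that with the criteria data the study holds or gathers. Unrecognised ABPA *can* bias the main contrast toward the hypothesis if it is commoner in the fungal group than in controls. The documents do not show that it *will*.

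The size is assumed throughout. One mislabelled patient in ten does little; two or three matter more. Confidence is high in the textual gap and low in the magnitude. The change is worth making because it costs almost nothing and protects the qualifier on which the study's conclusion depends.

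**What to change.** 1. Delete *if applicable* from the case report form item. Complete the protocol's own minimum-criteria checklist for every participant in all three groups, from the medical record plus the visit total IgE and m13. Do this before cytokine results are seen, and mark components that are not available. The checklist serves the analysis; it is not a proposal about care.
2. Keep the enrolled groups as the main analysis.
3. Pre-state one sensitivity analysis of fungal infection v control that leaves out any participant, in either group, who meets the full minimum criteria.
4. Results without participants who have total IgE above 500 IU/mL and positive m13 may be shown descriptively, with the same rule in both groups. They must not gate the conclusion.

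The cost is one form instruction, a record check on 25 patients and one repeat analysis, with the small loss of precision shown in step 6 of the working. Where imaging or precipitin/IgG was never obtained the checklist will stay incomplete, and the report should say for how many.
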